Source(s) of monetary or material support	National Institute for Health and Care Research (NIHR)	
Primary Sponsor	Intensive Care National Audit and Research Centre (ICNARC)	
Contact for public queries	[contact]	
Contact for scientific queries	[contact]	
Countries of recruitment	United Kingdom	
Health condition(s) or problem(s) studied	Paediatric critical care.	
Setting	19 UK Paediatric Intensive Care Units (PICUs)	
Intervention(s)	The intervention is no routine measurement of gastric residual volume (GRV). Standard unit feeding protocols will be followed but without GRV measurement to guide enteral feeding. The comparator is regular at least 6 hourly measurements of gastric residual volume. Standard unit feeding protocols will be followed, and enteral feeding will be guided by at least 6 hourly gastric residual volume (GRV) measurements.	
Inclusion and exclusion criteria	 POPULATION Children admitted to paediatric intensive care units who are receiving invasive mechanical ventilation, enrolled within 24 hours of first meeting the below eligibility criteria: INCLUSION CRITERIA: Aged ≥ 37 weeks corrected gestational age and < 16 years at the time of recruitment Receiving invasive mechanical ventilation (with extubation not planned in the next 48 hours) Intention to start feeding via the gastric route (including gastrostomy) EXCLUSION CRITERIA: Post pyloric feeding or jejunostomy End-of-life care plan in place with limitation of resuscitation Children on long term mechanical ventilation Current or recent gut pathology or surgery (e.g., necrotising enterocolitis (NEC), active GI bleeding, or any intestinal surgery) 	

Data category	Information			
	 Known to have been enrolled in the GASTRIC-PICU trial in the last 6 months. 			
Study type	Multi-centre, randomised, noninferiority, open-label trial with inbuilt pilot phase (with clear stop/go progression criteria to full trial) and health economic evaluation and patient follow-up 6 months.			
Date of first enrolment	May 2023			
Target sample size	4,700			
	The two clinical co-primary outcomes are:			
Primary outcomes	 Composite outcome of survival and days free from mechanical ventilation at 30 days (non-inferiority), and Percentage of the child's estimated energy requirements achieved by 72 hours after randomisation (superiority). 			
	The primary outcome of cost-effectiveness analysis is incremental net monetary benefits at six months.			
Secondary outcomes	 Time to achievement of target energy requirement Time to achievement of target protein requirement Diagnosis of Ventilator Associated Pneumonia (VAP) Diagnosis of necrotising enterocolitis (NEC) in infants Duration of time with no enteral feed in the first 7 days after randomisation Incidence of vomiting leading to feed stoppage in the first 7 days after randomisation Incidence of vomiting leading to feed stoppage in the first 7 days after randomisation Documented healthcare acquired infections Length of PICU stay and hospital stay Mortality at 30 days and 6 months Resource use and costs Health-related Quality of Life (assessed using PedsQL and CHU-9D questionnaire data) Quality-Adjusted Life Years (QALYs) Feeding component of the Functional Status Score 			
Economic outcomes	The economic analysis will also perform a cost-consequence analysis and report incremental costs alongside primary clinical outcome at 30 days.			

5. Abbreviations

CEA	Cost effectiveness Analysis		
CDC	Centre for Disease Control		
CICU	Cardiac Intensive Care Units		
CLABSI	Catheter Related Blood Stream Infections		
CRF	Case Report Form		
CRN	Clinical Research Network		
CYAG	Children's and Young People's Group		
DMEC	Data Monitoring and Ethics Committee		
ECLS	Extra Corporeal Life Support		
EN	Enteral Nutrition		
FSS	Functional Status Score		
GA	Gestational Age		
GI	Gastrointestinal		
GRV	Gastric Residual Volume		
IRAS	Integrated Research Application System		
HCAI	Healthcare Acquired Infection		
HRA	Health Research Authority		
HRQoL	Health Related Quality of Life		
HTA	Health Technology Assessment (Funding Stream of the NIHR		
INVOLVE	National advisory group that supports public involvement in health & social care research		
NBM	Nil by mouth		
PAG	Patient Advisory Group		
PedsQL	Pediatric Quality of Life Score		
PCCS	Paediatric Critical Care Society		
PCCS-SG	Paediatric Critical Care Society – Study Group		
PD	Peritoneal dialysis		
PICANet	Paediatric Intensive Care Audit Network		
PICU	Paediatric Intensive Care Unit		
PIS	Participant/Parent Information Sheet		
PPIE	Patient and Public Involvement and Engagement		
NEC	Necrotising Enterocolitis		
NICU	Neonatal Intensive Care Unit		
QALYs	Quality of Life adjusted Years		
SAP	Statistical Analysis Plan		
SSI	Surgical Site Infections		
TSC	Trial Steering Committee		
UK	United Kingdom		
VAP	Ventilator Associated Pneumonia		

6. Trial Flowchart

7. Background and Rationale

Underfeeding and inadequate delivery of nutrition remain a problem in paediatric intensive care units (PICUs) worldwide. A large international study of children in 31 PICUs showed only 37% of children received their required energy intake (1). On average, children in PICUs receive less than half of their predicted energy requirements (1). Inadequate energy delivery to critically ill infants and children has deleterious consequences. Inadequate nutrition has been associated with prolonged mechanical ventilation, impaired wound healing (including time to sternal closure following cardiac surgery in babies), increased healthcare acquired infections, longer PICU stays and increased mortality (1-6). Interruptions to the delivery of enteral nutrition (EN) are identified as the most significant preventable reason for inadequate energy achievement in the PICU (7, 8). These interruptions occur for several reasons, but the most common of these is feed intolerance as defined by a 'high gastric residual volume' (GRV) (7, 9). This practice of GRV measurement is routine and widespread in UK PICUs (8). GRV is obtained by aspirating the child's stomach contents via a nasogastric tube and is typically performed 4-6 hourly. However, the ability of these GRV measurements to predict feed intolerance is not established.

The rationale for GRV measurement is based on mitigating the perceived risk of pulmonary aspiration (from an overdistended stomach) in mechanically ventilated patients (10), but this risk remains unquantified and has been challenged in adults and neonates (11-14) (but not in children so far), suggesting the inaccuracy of this technique to assess feeding tolerance. A systematic review in critically ill adults did not find measuring GRV reduced the risk of Ventilator Associated Pneumonia (VAP) or aspiration (14). However, adult studies showed that not measuring GRV did significantly improve the achievement of energy goals.

20,000 children aged 0-17 years were admitted to UK PICUs between 2016-2018. Around half of these were less than one year old (15). PICU is an expensive service with the average cost per day of > £2000 (16), so any intervention that has the potential to reduce the length of time spent on organ support in PICU is beneficial both for the child and family and for the health service. Intensive care nurse workload is also an area of increased scrutiny, given nurses are the largest human cost in a PICU, therefore reducing nursing workload by removing any unnecessary practice would be beneficial. Furthermore, as 96.5% children now survive critical illness in the UK (15), ensuring the best possible outcomes is paramount. We know that nutritional deterioration *during* critical illness is frequent and intense (17) with both short- and long-term consequences. Thus, the effect of this practice may increase as PICU stay increases. This is important because the proportion of long-stay PICU patients in UK PICUs (and corresponding bed days) has increased significantly in the last 15 years (18).

7.1 Review of Existing Evidence

Our feasibility work found that GRV (gastric residual volume) is undertaken in nearly all UK PICUs (8). Yet, despite the prevalence of this practice, the evidence for it reflecting feed tolerance is poor, and GRV has not been shown to correlate to delayed gastric emptying (19). The measurement of GRV itself has also been shown to be inaccurate and unreliable, being affected by the position of the feeding tube in the stomach, the patient position, the feeding method used, the nurses' technique of aspiration and the feeding tube and syringe sizes used (20). The most recent study (21) also showed that aspiration of the NGT to obtain GRV in critically ill children is inaccurate (using gastric ultrasound) and in 70% of cases did not empty the stomach. Furthermore, what volume constitutes an 'acceptable' level of GRV also remains unknown and based on little or no evidence, with arbitrary values being used to define this (7, 8). Despite GRV being routinely measured in nearly all UK PICUs (8), it is not a standard practice in French PICUs. We conducted an observational pilot study in 2015-2016 to compare practices and outcomes in a UK PICU which routinely measures GRV to a French PICU that does not (22). We found no significant differences in VAP or adverse events, and a trend towards more consistent achievement of target energy goals as the PICU length of stay increased. However, as this was a retrospective study with a small sample size, this limited our ability to draw robust conclusions.

In summary, a distinct lack of evidence exists to support the routine practice of GRV monitoring to guide enteral feeding in critically ill children, with both increasing preterm neonatal and adult research showing this practice is unnecessary and can worsen nutritional delivery (11-14). However, critically ill children are distinctly different to adults and preterm neonates and these data cannot be extrapolated, given the marked differences in age, size, pathology, and clinical endpoints. At least half of children admitted to PICU are less than 12 months of age (23) compared with the mean age of adults in UK ICUs of around 70 years with multiple comorbidities (24). More importantly, the incidence of VAP in adult ICU is much higher (21.3 per 1000 ventilator days) (11, 12) compared to that in PICUs at 5.6 – 9.2 per 1000 ventilator days (25). A specific study in critically ill children is therefore urgently needed to confirm the findings found in other critically ill populations.

7.2 Potential Adverse Effects of Routine Gastric Residual Volume (GRV) Measurement

- Impaired achievement of estimated energy and protein requirements, which may impact on clinical outcomes, prolong mechanical ventilation duration and length of PICU stay.
- Discomfort/damage to gastric mucosa a key concern to parents (16).
- Depletion of gastric secretions and electrolyte disturbances where gastric residuals are frequently discarded.
- Unnecessary use of registered nurses' time.
- Increased costs related to disposables used to measure GRV.

7.3 Feasibility Work

Our team conducted the HTA-funded feasibility GASTRIC study that help inform the current commissioned call (20/128). Feeding intolerance, almost always defined by a 'high GRV' (8), is the most common reason in the decision to stop or withhold enteral nutrition (7, 9). This is a potentially modifiable factor, which could impact on nutritional delivery, clinical outcomes, and costs. With increasing evidence in adults and neonatal intensive care (11-14) it is now timely to examine the clinical and cost-effectiveness of this practice in critically ill children. The research is needed now because a high proportion of the ~20,000 children admitted to PICU in the UK annually are exposed to this procedure without any evidence of its risks and benefits. As the practice is so embedded into clinical practice, robust trial evidence is required to quantify the impact of this practice and determine whether this practice should be stopped. This has the potential to improve patient outcomes, reduce costs and save nursing time. Furthermore, if this practice is found to be unnecessary in this higher risk group of children, then this may have much broader implications and benefits for all tube-fed children. This trial is feasible now because of the track record of the Paediatric Intensive Care Society Group (PICS-SG) undertaking pragmatic clinical trials, such as FiSh (IRAS 195544), FEVER (IRAS 209931), SANDWICH (IRAS 209448), Oxy-PICU (IRAS 272768) and PRESSURE (IRAS 289545).

8. Aims, Objectives and Outcome Measures

8.1 Aim

To determine the clinical and cost-effectiveness of NO routine gastric residual volume (GRV) measurement to guide enteral feeding and to determine if it is non-inferior to standard at least 6 hourly gastric residual volume measurement in mechanically ventilated children admitted to PICU.

8.2 Objectives

Primary clinical objective is to determine whether no routine GRV measurement is non-inferior to at least 6 hourly GRV measurements to guide enteral feeding in critically ill ventilated children in PICU in terms of a composite outcome of survival and days free from mechanical ventilation (non-inferiority) and superior in terms of energy target achievement (superiority).

Primary health-economic objective is to conduct a full economic evaluation to assess the relative costeffectiveness of these two practices.

Secondary objectives are to compare non-routine measurement with regular up to 6 hourly measurements in terms of other important patient and family centred outcomes and cost.

8.3 Outcome Measures

8.3.1 Primary Outcome Measures

The two clinical co-primary outcomes are:

- Composite outcome of survival and days free from mechanical ventilation at 30 days from randomisation (non-inferiority), and
- Percentage of the child's estimated energy requirements achieved by 72 hours after randomisation (superiority).

The primary outcome of cost-effectiveness analysis is incremental net monetary benefits at six months.

8.3.2 Secondary Outcome Measures

Secondary outcomes during PICU stay:

- Time to achievement of target energy requirement
- Time to achievement of target protein requirement
- Diagnosis of Ventilator Associated Pneumonia
- Diagnosis of necrotising enterocolitis in infants
- Duration of time with no enteral feed in the first 7 days after randomisation
- Incidence of vomiting leading to feed stoppage in the first 7 days after randomisation
- Documented healthcare acquired infections

Secondary outcomes assessed at PICU discharge:

• Length of PICU stay (days)

Longer terms secondary outcomes (post-PICU discharge):

- Mortality at 30 days and 6 months post randomisation
- Length of hospital stay
- Health-related Quality of Life (assessed using PedsQL and CHU-9D questionnaire data)
- Feeding component of the Functional Status Score

These outcomes are consistent with core outcomes recommended for PICU trials (26) and this is consistent with our feasibility work consulting with parents and clinicians.

Cost-effectiveness outcomes

- Resource use and costs
- Total costs at six months.
- Quality-Adjusted Life Years (QALYs) at six months.
- Incremental net monetary benefits calculated at £20,000 per QALY at six months associated with intervention (No routine GRV measurement) versus control (standard GRV measurement).

8.3.3 Outcome Definitions

NECROTISING ENTEROCOLITIS (NEC): as a new diagnosis after randomisation for children who are under 1 year old. The diagnosis is to be based on a combination of systemic, abdominal and/or radiological signs.

- Systemic signs Include temperature instability, apnoea, bradycardia, raised inflammatory markers, thrombocytopenia, shock features. In NEC these are present with abdominal and or radiological signs stated below.
- Abdominal Intestinal signs include abdominal distension, reduced or absent bowel sounds, larger than normal gastric aspirates, gastric bleeding, rectal bleeding, abdominal tenderness, or cellulitis.
- Radiological signs The following are radiological signs of NEC and cases with these should be counted as a case of NEC: pneumatosis coli, portal gas, perforation – pneumoperitoneum (excluding air under the diaphragm associated with insertion of a PD catheter in theatre or in ICU, or accidental opening of the peritoneum during the operation).

A child who develops only mild systemic and/or abdominal-intestinal signs and is treated only with a 24-48 hour rule out course of NBM and antibiotics followed by re-starting feeds based on improvement should not be counted as a case of NEC.

If a general surgeon assesses the child and based on features from the systemic signs and abdominal signs elects to treat the child as NEC with NBM for minimum 5 days, then this case should be counted as a case of NEC.

Any child with a surgical abdomen who has a more serious picture – perforation, peritonitis, abdominal mass, is to be counted. There is no requirement for grading, however as a practical guide the following simplified classification has been suggested

- Moderate any child meeting the criteria who does not need surgery and survives.
- Severe a child with NEC who needs surgery and/or dies.

VENTILATOR ASSOCIATED PNEUMONIA (VAP): any new course of antibiotics prescribed for a presumed or proven VAP.

CATHETER RELATED BLOOD STREAM INFECTIONS (CLABSI): proven or suspected CLABSI leading to commencement or continuation of antimicrobials (Appendix 3).

SURGICAL SITE INFECTION (SSI): surgical site infection diagnosed within 30 days of the procedure, where the treating clinical team assesses the infection to be linked to the recent operation. A new course of antibiotics, or continuation of a current course for the clinical diagnosis of a surgical site infection. Surgical site infections also include those where a debridement or other surgical intervention is required to treat the infection.

ESTIMATED PROTEIN REQUIREMENT: 1.5g/kg (65% by 72 hours, 100% post-72 hours).

ESTIMATED ENERGY REQUIREMENT: estimated using the Schofield equation for age and gender (with no stress factors applied) (65% by 72 hours, 100% post-72 hours).

9. Trial Design and Setting

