12.1 Intervention

The intervention arm is **no routine GRV measurement** to guide enteral feeding.

Patients should be monitored for signs of feed intolerance using clinical signs only: vomiting and other gastrointestinal or systemic signs but **not** by using GRV.

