14.3 Recording and Reporting Procedures

The key safety outcomes in the GASTRIC-PICU trial are ventilator-associated pneumonia (VAP) and necrotising enterocolitis (NEC). Incidence of these events will be captured via the Case Report Forms and does not need to be reported additionally as SAEs.

Considering that all children eligible for the GASTRIC-PICU trial are critically ill and, due to the complexity of their condition, are at an increased risk of experiencing AEs – occurrences of SAEs will only be reported if they are considered to be possibly, probably or definitely causally related to the study (i.e., either as a consequence of measuring GRV, or not measuring GRV). Non-serious adverse events do not require reporting for trial purposes.

The reporting period is from the time of randomisation until 30 days post-randomisation or until final discharge from critical care unit (whichever is sooner).

All reportable SAEs (i.e., serious events which are considered possible, probably, or definitely related to the study) must be reported to ICNARC CTU within 24 hours of the site research team becoming aware of the event. Related events must be assessed for expectedness (against the list in Appendix 3). Staff should not wait until all information about the event is available before sending SAE notification. Information not available at the time of the initial report must be documented and submitted as it becomes available.

SAEs must be recorded in the patients' medical notes and reported to the ICNARC CTU using the GASTRIC-PICU SAE Reporting eCRF. If the eCRF is unavailable, the SAE report can be sent by email to [contact].

The process for recording and reporting adverse events and serious adverse events is summarised in Figure 1 (Adverse Event Reporting).

Figure 1. Adverse Event Reporting

*If there is any uncertainty about whether the SAE is associated with trial treatment, then it should be reported.

On receipt of an SAE report, a member of the ICNARC CTU will first evaluate the report for completeness and consistency. Then, a clinical member of the GASTRIC-PICU Trial Management Group (TMG) will evaluate the event to determine whether it requires expedited reporting to the Research Ethics Committee (REC). If the event is a related and unexpected SAE, the ICNARC CTU will submit a report to the REC within 15 calendar days.

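### The NEC definition uses gastric aspirate size, which only the control arm measures routinely: a structural risk of uneven ascertainment that favours no-GRV, of unknown and possibly small size

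*Protocol*

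**What the plan says.** Section 8.3.3 (Outcome Definitions) limits the outcome to new diagnoses after randomisation in children under one year. Its general rule is: "The diagnosis is to be based on a combination of systemic, abdominal and/or radiological signs". The abdominal list has seven entries, among them "reduced or absent bowel sounds, larger than normal gastric aspirates, gastric bleeding"; the other four are distension, cellulitis, tenderness and bleeding from the rectum.

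More specific counting rules follow:

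- Pneumatosis, portal gas and perforation are "radiological signs of NEC and cases with these should be counted as a case of NEC".
- A case counts when the assessing surgeon, "based on features from the systemic signs and abdominal signs elects to treat the child as NEC with NBM for minimum 5 days".
- A surgical abdomen with a more serious picture counts.
- A child with only mild systemic or abdominal signs who "is treated only with a 24-48 hour rule out course of NBM and antibiotics followed by re-starting feeds based on improvement should not be counted" is left out.

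On what is observed in each arm, section 12.1 states for no-GRV: "Patients should be monitored for signs of feed intolerance using clinical signs only". It rules out GRV for this purpose. Section 12.2 requires GRV at least every 6 hours in the control arm. Section 9.2, in defining non-adherence, exempts a measurement made in the no-GRV arm for a recorded clinical indication.

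Section 14.3 names NEC, with VAP, as a key safety outcome. It is captured on the CRF and need not also be reported as an SAE. Section 16.3.3 compares NEC between arms by adjusted logistic regression. Section 12.4 states that the trial is not blinded.

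**The concern.** An outcome definition should give both arms the same opportunity to become a case. Here one input to the definition is the measurement that randomisation switches on or off. A control infant is checked for a large aspirate several times a day. A no-GRV infant is checked only if something else prompts it.

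This can act in two ways. A large aspirate in a control child may complete the set of signs on which the child is labelled and treated as NEC. In the no-GRV arm, the absence of that observation may leave a similar child unsuspected or unlabelled. Both lower the NEC ratio of no-GRV to control, so both make the intervention look safer.

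At stake is the comparison meant to reassure clinicians that dropping the measurement does not harm infants. The protocol also gives its own reason to distrust the sign: section 7.1 describes GRV measurement as inaccurate and says that no acceptable level is known. The definition sets no threshold for a large aspirate.

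**Working it through.** The protocol states no NEC rate, margin or power, so there is no figure to reproduce. The check is a reading of the routes, followed by an illustration on assumed values.

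**Step 1. Where aspirate size can enter (section 8.3.3)**

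| Route | Can aspirate size decide whether the case counts? |
|---|---|
| Radiological sign | No. It could matter only earlier, through who is investigated |
| Surgical abdomen | No |
| Surgeon treats as NEC, nil by mouth at least 5 days, on systemic and abdominal signs | Yes, as one of the abdominal signs |
| Mild signs with a 24-48 hour rule-out course only | Not counted in either arm |
| General rule on a combination of signs | Possibly; the minimum combination is not specified |

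The exposure is therefore mainly the surgeon-decided route without radiology, plus differences in suspicion and work-up.

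**Step 2. What each arm can observe.** Control: aspirates at least 6-hourly (12.2). No-GRV: not routine (12.1), but tolerated on clinical indication (9.2). The opportunity to see the sign is unequal, but it is not zero in the no-GRV arm.

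**Step 3. Direction and possible size.** Let f be the share of NEC cases that can be counted only through the clinical-sign route. Let s be the detection of those cases in the no-GRV arm relative to control. For every case counted in control under equal true risk, the no-GRV arm counts (1 - f) + f × s. Hence

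observed risk ratio = true risk ratio × [1 - f(1 - s)].

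Neither f nor s is in the protocol; the values below are assumptions. With a true risk ratio of 1:

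| f | s | Observed risk ratio | True ratio that would show as 1.0 |
|---|---|---|---|
| 0.1 | 0.95 | 1 - 0.1 × 0.05 = 0.995 | 1/0.995 = 1.005 |
| 0.3 | 0.80 | 1 - 0.3 × 0.20 = 0.94 | 1/0.94 = 1.06 |
| 0.5 | 0.60 | 1 - 0.5 × 0.40 = 0.80 | 1/0.80 = 1.25 |

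Whenever s is below 1 the factor is below 1, so this mechanism favours no-GRV throughout. Its size runs from negligible to material, and the protocol does not say where the trial would lie.

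**The case against.** The strongest reply is that very few cases can hang on the aspirate. It is one of seven abdominal signs, and a combination is required. Radiological and surgical-abdomen cases count without it. Short rule-out courses, which an isolated large aspirate might well prompt, are excluded. To qualify through the surgeon route on the aspirate alone, a child would need systemic signs, none of the other six abdominal signs, no radiological sign, and still at least 5 days nil by mouth. Suspected NEC could itself be a clinical indication for measuring GRV in the no-GRV arm. NEC is also a secondary outcome in infants, and the non-inferiority decision rests on death and ventilator-free days, which do not use this definition.

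All of that stands as a limit on size. It does not make the definition neutral between arms, and the protocol gives nothing from which the remainder could be judged small.

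Two stronger readings are tempting, and the document supports neither. A reader might infer that NEC will in fact be detected more readily in controls. The text shows an unequal opportunity, not a demonstrated difference. A reader might also set s to zero, so that the ratio becomes 1 - f. With f of 10-30% this gives 0.90 to 0.70, hiding a true excess of 11-43% (1/0.90 = 1.11; 1/0.70 = 1.43). That requires every such case to be missed under no-GRV, which sits badly with the exemption in section 9.2, and the 10-30% has no source in the protocol.

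A further fair objection is that deleting the sign from the list would achieve little, because the surgeon would still have seen the aspirate and the treated case would still count. This stands, and it shapes the fix.

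**Conclusion.** The point holds as a structural risk. The definition of a named key safety outcome includes a sign that one arm looks for routinely and the other only on indication, in an open-label trial. Any distortion from this source favours no-GRV. It is confined mainly to cases without radiological signs or a surgical abdomen, and does not touch the co-primary outcomes.

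The size cannot be stated. The illustrative ratios of 0.995 to 0.80 rest wholly on assumed values of f and s and should not be cited as an estimate. The effect may prove small.

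The point should still be settled in the protocol. Section 8.3.3 fixes what counts as a case, and a later analysis can separate aspirate-dependent cases only if the supporting signs were recorded. The statistical analysis plan is not at hand and may already contain a confirmed-NEC analysis; that would help but would not change the definition.

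**What to change.** For the trial endpoint only, and identically in both arms:

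- In section 8.3.3, count a case as trial NEC only if it has a radiological sign, a surgical abdomen, or at least one abdominal sign that does not depend on gastric aspiration. Apply this to surgeon-treated cases too. State how gastric bleeding seen only in an aspirate is to be classed, since it also depends on aspiration.
- Record on the NEC page of the CRF which signs supported the diagnosis.
- Report a sensitivity analysis restricted to radiologically or surgically confirmed NEC.

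Clinical diagnosis and care stay as they are; only the classification for the comparison changes.

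The cost is a short edit to one definition, one CRF page and one added analysis. Some cases labelled NEC by clinicians will not count as trial NEC. Differences in suspicion and work-up between open arms are reduced, not removed, because a large aspirate may still lead to the investigation that reveals another sign.
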